- The antihyperglycemic medication dose would be considered for reduction in the event of 1 documented and otherwise unexplained hypoglycemic event (blood glucose concentration <65 mg/dL) or 2 undocumented and otherwise unexplained suspected hypoglycemic events between any 2 scheduled visits. For subjects on more than 1 antihyperglycemic medication, it is recommended to reduce insulin first (if applicable), then the oral and/or other injectable antidiabetic agents. If the previous criteria are met again following dose reduction, further dose reductions or cessation of 1 or more antihyperglycemic agents, are suggested. See [Section 9.5.4.2](#) for the definition and reporting of hypoglycemic events.

To minimize the risk of cardiac valve toxicity, subjects must not initiate use of agents that have documented correlation with increased incidence of valvulopathy and/or pulmonary hypertension (eg, pergolide, ergotamine, methysergide, or cabergoline) during the study. If any of the above agents are clinically warranted, and subjects initiate any of these agents, lorcaserin HCl should be discontinued but can be restarted on lorcaserin HCl after being off the medications above for 1 month. Otherwise, the study medication should not be restarted, but the subject should continue all study visits. (revised per Amendment 03)

Assessments**Efficacy Assessments**

- Body weight and height will be measured to calculate BMI; BMI will then be used to calculate the proportion (%) of subjects achieving at least a 5% and at least a 10% BMI reduction
- Waist circumference (revised per Amendment 03)
- Total body fat mass and total body lean mass will be determined centrally using DEXA in a subset of subjects (selected prior to randomization at selected sites) at baseline and Week 52/EOT (revised per Amendment 03)
- Measurement of systolic and diastolic BP, heart rate (taken after resting for 5 minutes), fasting lipids (total cholesterol, HDL cholesterol, LDL cholesterol, and triglycerides), fasting plasma glucose, fasting insulin, HbA_{1c}, and Homeostasis Model Assessment of Insulin Resistance (HOMA-IR) to assess cardiovascular and metabolic risk profiles from baseline to Week 52 (revised per Amendment 03)
- Prehypertension and primary hypertension as defined by the Expert Panel on Integrated Guidelines for Cardiovascular Health and Risk Reduction in Children and Adolescents
- Dyslipidemia as defined by the Expert Panel on Integrated Guidelines for Cardiovascular Health and Risk Reduction in Children and Adolescents

Every effort will be made to ensure that at least 80% of randomized subjects will have an assessment of the primary efficacy endpoint regardless of whether or not the subject remained on study drug or completed other study assessments. (revised per Amendment 03)

Pharmacokinetic Assessments

Blood samples (approximately 4 mL each) for PK assessment will be collected at Weeks 12, 28, 36, and 52 for analysis of Population PK. (revised per Amendment 01)

On the day of the Week 12, 28, and 52 clinic visits, subjects will be instructed not to take their study drug at home before the visit, but to bring their study drug to the clinic visit, and take their daily dose **at the clinic**. Two blood samples for determination of plasma concentrations of lorcaserin will be taken: 1 predose (within 30 minutes before dosing), and 1 within 1 to 3 hours after dosing. Dose times must be recorded for the last 2 dosing times before the day of clinic visit. Week 52 PK samples should only be collected if the sample can be drawn within 60 hours of the last dose of study drug. (revised per Amendment 01)

On the day of the Week 36 clinic visit, subjects will take their study drug in the morning **at home**, and will be asked to visit the clinic within 4 to 6 hours of dosing that day, during which 1 blood sample for PK assessments will be collected. Dose times must be recorded for the last 2 dosing times prior to the clinic visit. (revised per Amendment 01)

Pharmacodynamic Assessments

- Change from baseline in BMI
- Proportion (%) of subjects achieving at least a 5% and at least a 10% reduction in BMI

Other PD endpoints will be considered based on the data at the end of the study to explore their relationships with lorcaserin plasma exposure.

Pharmacogenomic/Pharmacogenetic Assessments

Not applicable

Safety Assessments

Safety assessments will consist of monitoring and recording all adverse events (AEs) and serious adverse events (SAEs); electrocardiograms (ECGs); laboratory evaluation for hematology, metabolic function (fasting plasma glucose, fasting lipids, and thyroid), adrenal function and biochemical blood and urine bone health assessments; blood chemistry and urine values; neuropsychiatric events; periodic measurement of vital signs, neuromuscular signs for screening potential serotonin syndrome, and signs or symptoms of priapism and hyperprolactinemia; and performance of physical examinations. In subjects with potential prolactin-related AEs, such as

galactorrhea, changes in libido, or changes to menstrual cycle, fasting prolactin level will be measured and assessed.

Other Safety Assessments

Effect on growth will be evaluated using the CDC growth chart and bone age determination by x-ray of the hand. Sexual maturation will be evaluated by assessing sex hormones and Tanner Staging.

The C-SSRS will be used to assess all subjects in the study for any signal of depression or suicidal ideation or behavior at every visit. Additionally, screening, diagnosing, monitoring, and measuring the severity of depression will be assessed using the PHQ-9 and effects on cognition will be assessed using the Leiter-3. (revised per Amendment 01)

Bone mineral density and content, total body fat mass and total body lean mass will be determined using DEXA in a subset of subjects (selected prior to randomization at selected sites). (revised per Amendment 03)

Echocardiographic assessments will be used to exclude subjects with US Food and Drug Administration (FDA)-defined valvulopathy, pulmonary hypertension, and other major cardiovascular disease (as outlined in [Exclusion Criterion No. 4](#)) during the Screening Period. Additionally, cardiac valvular function and pulmonary systolic pressure changes at Weeks 28 and 52 will be assessed. Valvular regurgitation as assessed in the echocardiogram will be rated absent, trace, mild, moderate, or severe for the aortic, mitral, and tricuspid valves; the rating will be absent or present for the pulmonic valve. The evaluations will be based on guidelines from the American Society of Echocardiography. Pulmonary artery pressure will be estimated from the TR jet velocity. (revised per Amendments 03 and 04)

Bioanalytical Methods

Lorcaserin will be quantified in plasma using a validated liquid chromatography coupled with tandem mass spectrometry.

Statistical Methods

Study Endpoints

Primary Efficacy Endpoint

- Change in BMI from baseline to Week 52

Key Secondary Efficacy Endpoint

- Proportion (%) of subjects achieving at least a 5% BMI reduction at Week 52

Other Secondary Efficacy Endpoints

- Proportion (%) of subjects achieving at least a 5% BMI reduction at Week 12
- Proportion (%) of subjects achieving at least a 10% BMI reduction at Week 52
- Percentage change in BMI from baseline to Week 52
- Association between change and percentage change in BMI from baseline to Week 52 with the outcome of achieving at least a 5% BMI reduction at Week 12 (revised per Amendment 02)
- Association between the proportion (%) of subjects achieving at least a 5% or 10% BMI reduction at Week 52 with the outcome of achieving at least a 5% BMI reduction at Week 12 (revised per Amendment 02)
- Change in waist circumference from baseline to Week 52
- Change in total body composition (total fat and lean mass) in a subset of randomized subjects at end of 52 weeks of treatment (revised per Amendment 03)
- Change in HbA_{1c} from baseline to Week 52 for subjects with T2DM at baseline (revised per Amendment 03)
- Change in fasting plasma glucose, fasting insulin, and HOMA-IR from baseline to Week 52 for subjects

with T2DM at baseline (revised per Amendments 03 and 04)

- Change in fasting plasma glucose, fasting insulin, and HOMA-IR from baseline to Week 52 for the subjects without T2DM at baseline (revised per Amendments 03 and 04)
- Change in BP (systolic and diastolic) and heart rate from baseline to Week 52
- Change in fasting lipid profile (total cholesterol, LDL cholesterol, HDL cholesterol, triglycerides) from baseline to Week 52
- Proportion (%) of subjects with prehypertension or primary hypertension at Week 52
- Proportion (%) of subjects with dyslipidemia at Week 52
- Subjects compliance rate at each visit by pill count during 52 week treatment (revised per Amendment 03)

Analysis Sets

- The Safety Analysis Set is the group of subjects who received at least 1 dose of study drug and had at least 1 post dose safety assessment.
- The Full Analysis Set (FAS) is the group of all randomized subjects regardless of adherence to study drug.
- Per-Protocol Analysis Set (PP) is the group of all randomized subjects who are 80% or greater compliant with study medication, completed the study, have no major protocol deviations, have no violations of inclusion or exclusion criteria, and have BMI data at baseline and Week 52. The determination of subjects to be excluded from this population based on the above criteria and a list of major protocol violations will be included in the statistical analysis plan (SAP) and finalized before data base lock.
- The PD Analysis Set is the group of subjects who had sufficient PD data to derive at least 1 PD parameter.
- The PK Analysis Set is the group of all randomized subjects from whom at least 1 valid lorcaserin plasma concentration was obtained with associated documented dosing history.
- The population PK/PD set is the group of randomized subjects with PK information and who have at least 1 adequately documented measurement of BMI.

Efficacy Analyses

The FAS will be used as the primary analysis set for all efficacy analyses, and the PP will be used as a supportive analysis. Unless otherwise specified, a 2-sided $\alpha=0.05$ significance level will be used in all efficacy analyses.

Primary Efficacy Analysis

The primary efficacy endpoint is the change in BMI from baseline to Week 52. The change from baseline in BMI will be analyzed using analysis of covariance model (ANCOVA) with factors of treatment, sex (male and female) as fixed effect, and the baseline age and BMI as covariates. The missing values will be imputed using a pattern mixture model utilizing multiple imputation (MI) assuming the missing values are missing not at random (MNAR). The missing values will be imputed at each visit using all available values including the retrieved measurement from the postdiscontinuation data. The details of the analysis model and missing value imputation method will be further described in the SAP.

In addition, the following analyses will also be considered as sensitivity analyses:

- PP analysis: The same primary efficacy analyses described above will be repeated based on the PP.
- Change from baseline in standardized BMI score (Z-score): The same primary efficacy analyses described above will be repeated using Z-score.

Subgroup analyses and additional sensitivity analyses, if appropriate, may also be performed and will be described in the SAP.

Key Secondary Efficacy Analyses

The key secondary efficacy endpoint is the proportion of subjects achieving at least a 5% BMI reduction at

Week 52. The secondary efficacy endpoint will be analyzed only if the test for the primary efficacy endpoint is statistically significant.

The proportion of subjects achieving at least a 5% BMI reduction at Week 52 will be analyzed using a logistic regression model with factors of treatment, sex (male and female), and baseline BMI as a covariate using FAS. Subjects with any missing assessment at Week 52 will be considered as treatment failures in this analysis.

Other Secondary Efficacy Analyses

Unless specified, for all other secondary efficacy endpoints, the continuous variables will be analyzed using mixed effect model repeated measurement analysis (MMRM) and categorical variables will be analyzed using the Cochran Mantel Haenszel test, Chi-square test, or logistic regression as appropriate. Additional analysis may be performed as needed using appropriate statistical methodologies as specified in SAP.

Subgroup analyses will be performed on the primary efficacy endpoint, including sex (male and female), and race (American Indian or Alaska Native, Asian, Black or African American, Native Hawaiian or other Pacific Islander, or White) and age. Additional subgroups may be explored, if deemed necessary.

No adjustment for multiplicity is planned for other secondary endpoints, subgroup, and sensitivity analyses.

Pharmacokinetic Analyses

Lorcaserin plasma concentration-time data will be subjected to population PK analysis using nonlinear mixed effects modeling. The effect of covariates such as baseline characteristics or demographics on PK will be explored. Derived exposure parameters such as the maximum observed concentration and the area under the concentration-time curve from time 0 to 24 hours at steady-state will be calculated from the final PK model using individual posterior estimates of the PK parameters and from dosing history. The PK analysis set will be used for this analysis.

Pharmacodynamic Analyses

Change from baseline in BMI will be assessed as the PD endpoint. The PD analysis set will be used for this analysis.

Other assessments (eg, percentage of BMI change, proportion [%] of subjects achieving $\geq 5\%$ and $\geq 10\%$ BMI reduction, and change in waist circumference from baseline) will also be assessed as part of the PD analysis. The PK/PD analysis set will be used for this analysis.

Pharmacokinetic/Pharmacodynamic Analyses

Population PK/PD modeling will be used to explore the relationship between lorcaserin plasma exposure and response, including but not limited to change in BMI from baseline and the probability of achieving at least a 5% and at least a 10% change in BMI from baseline to Week 52. Additionally, exposure-safety relationships for select safety parameters may be explored graphically depending on the data at the end of study. Any emergent relationship may be modeled as appropriate. Any parameters based on the study data may be considered for exploratory assessment for its relationship to PK.

Pharmacogenomic/Pharmacogenetic Analyses

Not applicable

Safety Analyses

Evaluations of safety will be performed on the Safety Analysis Set. Safety assessments including the incidence of AEs (including changes from baseline in physical examination, neuromuscular sign assessment for serotonin syndrome, and signs and symptoms of priapism and hyperprolactinemia), out-of-normal-range laboratory safety test values, change from baseline in laboratory safety test values, ECGs, vital sign measurements, bone mineral density and content, total body fat mass and total body lean mass by DEXA, FDA-defined valvulopathy, and pulmonary hypertension assessed by echocardiograph will be summarized by treatment group using descriptive statistics or frequency count as appropriate.

No hypothesis testing will be performed for the safety assessment. (Revised per Amendment 04)

Other Safety Analyses

In addition, cognition will be evaluated by the Leiter-3, depression will be evaluated by the PHQ-9, and suicidal ideation and behavior will be evaluated by the C-SSRS, and will also be summarized by treatment group using descriptive statistics or frequency count as appropriate. For echocardiographic assessments, the proportion of subjects who develop FDA-defined valvulopathy, the proportion of subjects who develop pulmonary hypertension [pulmonary hypertension is defined when the subject's systolic pulmonary artery pressure (SPAP) ≥ 40 mmHg evaluated by echocardiograph], and change from baseline in SPAP will be summarized by treatment group at Week 28 and Week 52 using descriptive statistics or frequency count as appropriate. (revised per Amendment 01)

No hypothesis testing will be performed for the safety assessment.

Study Day 1 for all safety analyses will be defined as the date of the first dose of study drug.

Interim Analyses

Not applicable

Sample Size Rationale

The proposed sample size is based on the comparison of the primary efficacy endpoint, change in BMI from baseline to Week 52 between the Belviq XR 20-mg treatment group and placebo group. Assuming a SD of 2.2 kg/m^2 and a 40% dropout rate, a sample size of 260 subjects in a 1:1 ratio ($n=130$ in the Belviq XR 20-mg treatment group; $n=130$ in the placebo group) will have at least 80% power to detect a treatment difference of 1 kg/m^2 in BMI, using a 2-sided t-test with $\alpha=0.05$. Assuming the proportion of subjects achieving at least a 5% BMI reduction at Week 52 is 20% for the placebo group and a 40% dropout rate, this sample of 260 subjects (130 subjects for Belviq XR 20 mg and 130 subjects for placebo) will also have greater than 78% power to detect an absolute difference of 20% between the Belviq XR 20-mg group and the placebo group, using a 2-sided Chi-Square test with $\alpha=0.05$. The assumption used in the sample size calculation is based on the 2 pivotal lorcaserin studies APD356-009 and APD356-011 in obese and overweight non-diabetic adult subjects. (revised per Amendment 02)

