In cases where an actual SPAP value is not measurable due to lack of adequate TR jet, the pulmonary flow acceleration time measured at the right ventricular outflow tract (RVOTAT), will be used to assess eligibility. Subjects with a RVOTAT ≤ 100 msec will be excluded, suggesting an elevated mean SPAP; eligibility for the those subjects with RVOTAT between 100 and 120 msec will be determined based on combined assessment of the TR jet, septal motion and right ventricular size.

- Left ventricular ejection fraction $< 45\%$
- Intracardiac mass, tumor or thrombus
- Evidence of congenital heart disease

- Clinically significant pericardial effusion (eg, moderate or larger or with hemodynamic compromise)
5. Significant renal or hepatic disease as evidenced by a serum creatinine greater than 1.5×upper limit of normal (ULN), serum transaminases greater than 3×ULN, or total bilirubin greater than 1.5×ULN in absence of Gilbert’s syndrome
 6. Any suicidal ideation with intent with or without a plan, at the time of or within 6 months of Screening, as indicated by answering “Yes” to questions 4 or 5 on the Suicidal Ideation section of the C-SSRS
 7. Any suicidal behavior in the past based on the C-SSRS (revised per Amendment 01)
 8. Any history of anorexia or bulimia within 2 years before Screening, Attention Deficit Hyperactivity Disorder (ADHD), any Diagnostic and Statistical Manual of Mental Disorders, 5th Edition (DSM-5) depressive disorder, suicidal ideation or behavior, bipolar disorder, or schizophrenia
 9. Known secondary causes (genetic, endocrine, or metabolic) for obesity (eg, Prader-Willi syndrome, Bardet Biedl syndrome, Down’s Syndrome, untreated hypothyroidism, Cushing’s syndrome, daily systemic corticosteroid exposure for longer than 30 days, history of significant exposure to corticosteroids for chronic illness during the past year; inhaled steroids will be allowed) (revised per Amendment 03)
 10. Use of other products intended for weight loss including prescription drugs, over-the-counter (OTC) drugs, and herbal preparations within 1 month before Screening
 11. Use of any of the following medications:
 - a) Serotonergic drugs within 7 days (or 5 half-lives, whichever is longer) or monoamine oxidase inhibitors (MAOIs) within 30 days before Randomization, including:
 - selective serotonin reuptake inhibitors (SSRIs)
 - serotonin norepinephrine reuptake inhibitors (SNRIs)
 - tricyclic antidepressants (TCAs)
 - bupropion
 - triptans
 - St. John’s Wort

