9.3 Selection of Study Population

Approximately 500 subjects will be screened to ensure that 260 subjects will be randomized. (revised per Amendment 02)

Subjects who do not meet all inclusion criteria or do meet any exclusion criteria will not be eligible to receive study drug. Subjects who screen fail can be rescreened only once and without repeating the screening echocardiogram for up to 90 days after the previous echocardiogram. All other screening assessments must be repeated when a subject is rescreened. Subjects that rescreen more than 90 days after the previous echocardiogram must repeat all screening assessments including the screening echocardiogram. (revised per Amendments 03 and 04)

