9.3.2 Exclusion Criteria

Subjects who meet any of the following criteria will be excluded from this study:

1. Clinically significant new illness within 1 month before randomization that may affect the subject's ability to fulfill the study requirements or significantly confound the assessments
2. Who cannot swallow investigational products
3. With T2DM who have hypoglycemia unawareness (revised per Amendment 03)
4. Any of the following findings on screening echocardiography:
 - Aortic regurgitation mild or greater
 - Mitral regurgitation moderate or greater
 - Mitral or aortic valve stenosis greater than mild (ie, aortic stenosis [AS]: jet > 3.0 m/s, mean gradient > 25 mm Hg, and aortic valve area [AVA] < 1.5 cm²; MS: mean gradient > 5 mm Hg and mitral valve area [MVA] < 1.5 cm²)
 - Systolic pulmonary artery pressure (SPAP) > 40 mm Hg (and/or tricuspid regurgitation (TR) jet velocity > 2.9 m/s)
 - In cases where an actual SPAP value is not measurable due to lack of adequate TR jet, the pulmonary flow acceleration time measured at the right ventricular outflow tract (RVOTAT), will be used to assess eligibility. Subjects with a

RVOTAT \leq 100 msec will be excluded, suggesting an elevated mean SPAP; eligibility for the those subjects with RVOTAT between 100 and 120 msec will be determined based on combined assessment of the TR jet, septal motion and right ventricular size.

- Left ventricular ejection fraction $<45\%$
 - Intracardiac mass, tumor or thrombus
 - Evidence of congenital heart disease
 - Clinically significant pericardial effusion (eg, moderate or larger or with hemodynamic compromise)
5. Significant renal or hepatic disease as evidenced by a serum creatinine greater than $1.5 \times$ upper limit of normal (ULN), serum transaminases greater than $3 \times$ ULN, or total bilirubin greater than $1.5 \times$ ULN in absence of Gilbert's syndrome
 6. Any suicidal ideation with intent with or without a plan, at the time of or within 6 months of Screening, as indicated by answering "Yes" to questions 4 or 5 on the Suicidal Ideation section of the C-SSRS
 7. Any suicidal behavior in the past based on the C-SSRS (revised per Amendment 01)
 8. Any history of anorexia or bulimia within 2 years before Screening, Attention Deficit Hyperactivity Disorder (ADHD), any Diagnostic and Statistical Manual of Mental Disorders, 5th Edition (DSM-5) depressive disorder, bipolar disorder, or schizophrenia

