 9. Known secondary causes (genetic, endocrine, or metabolic) for obesity (eg, Prader-Willi syndrome, Bardet Biedl syndrome, Down's Syndrome, untreated hypothyroidism, Cushing's syndrome, daily systemic corticosteroid exposure for longer than 30 days, history of significant exposure to corticosteroids for chronic illness during the past year; inhaled steroids will be allowed) (revised per Amendment 03)
 10. Use of other products intended for weight loss including prescription drugs, over-the-counter (OTC) drugs, and herbal preparations within 1 month before Screening
 11. Use of any of the following medications:
 - a) Serotonergic drugs within 7 days (or 5 half-lives, whichever is longer) or monoamine oxidase inhibitors (MAOIs) within 30 days before Randomization, including:
 - selective serotonin reuptake inhibitors (SSRIs)
 - serotonin norepinephrine reuptake inhibitors (SNRIs)
 - tricyclic antidepressants (TCAs)
 - bupropion
 - triptans
 - St. John's Wort
 - tryptophan
 - linezolid
 - dextromethorphan in any form (eg, OTC cold medicines)
 - lithium
 - tramadol
 - antipsychotics or other dopamine antagonists

- b) Others
- antiseizure medications including valproic acid, zonisamide, topiramate and lamotrigine
 - oral steroids (topical and inhaled steroids are acceptable)
 - stimulant medications (Ritalin®, Concerta®, biphedamine and Dexedrine®)
 - benzodiazepines
12. Use of drugs known to increase the risk for cardiac valvulopathy within 6 months before Screening, including but not limited to pergolide, ergotamine, methysergide, and cabergoline
 13. History or evidence of clinically significant disease (eg, malignancy, cardiac, respiratory, gastrointestinal, renal, or psychiatric disease) other than prediabetes (impaired fasting glucose or impaired glucose tolerance), T2DM treated with oral antidiabetic agents (excluding sulfonylurea) or non-insulin injectable antidiabetic agents, obstructive sleep apnea, dyslipidemia, and nonalcoholic fatty liver disease
 14. Use of Belviq XR within 6 months before Screening or hypersensitivity to Belviq XR or any of the excipients
 15. Significant change in diet or level of physical activity within 1 month before dosing or change in weight of more than 5 kg within 3 months before Screening
 16. Any use of a of very-low-calorie (<1000 calories/day) weight loss diet within 6 months before Screening
 17. History of alcohol or drug dependence or abuse
 18. Recreational drug use within 2 years before Screening

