 19. Known to be human immunodeficiency virus (HIV) positive
 20. Known to have active viral hepatitis (B or C) (revised per Amendment 01)
 21. Malignancy within 5 years before Screening
 22. Unable to attend scheduled visits (eg, lack of transportation) or lack of a caregiver or guardian to supervise study participation
 23. Special needs subjects who are unable to comprehend study-related instructions (eg, mild to profound mental retardation [IQ <70], moderate to severe cognitive developmental delay, pervasive development disorders, autism)
 24. Ongoing epilepsy or other seizure disorder, or use of medications for a seizure disorder within 6 months of screening or any time between screening and randomization
 25. Subjects with a BP in the 95th percentile or greater for age, sex, and height on 2 separate readings recorded on 2 separate days. Those subjects who had uncontrolled hypertension at Screening can be rescreened more than 1 month after initiation or adjustment of antihypertensive therapy 1 time.
 26. Currently enrolled in another clinical study or has used any investigational drug or device within 30 days before providing informed consent

27. Planned bariatric surgery during the study or prior bariatric surgical procedures (revised per Amendment 03)
28. Not suitable to participate in the study in the opinion of the investigator, including consideration of any existing physical, medical, or mental condition that prevents compliance with the protocol
29. Female subjects who are breastfeeding or pregnant at Screening or Baseline (as documented by a positive β -human chorionic gonadotropin test). A separate Baseline assessment is required if a negative screening pregnancy test was obtained more than 72 hours before the first dose of study drug.
30. Female subjects of childbearing potential who:
 - a. Had unprotected sexual intercourse within 30 days before study entry and who do not agree to use a highly effective method of contraception (eg, total abstinence, an intrauterine device, a double-barrier method [such as condom plus diaphragm with spermicide], a contraceptive implant, an oral contraceptive, or have a vasectomized partner with confirmed azoospermia) throughout the entire study period and for 28 days after study drug discontinuation
 - b. Are currently abstinent, and do not agree to use a double-barrier method (as described above) or refrain from sexual activity during the study period and for 28 days after study drug discontinuation

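### Exclusion No. 8 bars past suicidal ideation in the synopsis but not in Section 9.3.2, so the protocol gives two answers on dosing a narrow group of adolescents

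*Protocol*

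**What the plan says.** Three criteria in each list deal with suicidality or psychiatric history.

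- **No. 6**, worded alike in the synopsis and Section 9.3.2, excludes "Any suicidal ideation with intent with or without a plan, at the time of or within 6 months of Screening". It identifies these subjects by a positive answer to "questions 4 or 5 on the Suicidal Ideation section of the C-SSRS".
- **No. 7**, also alike in both, excludes "Any suicidal behavior in the past based on the C-SSRS".
- **No. 8** opens the same way in both lists, with eating disorders (limited to 2 years before Screening) and attention deficit hyperactivity disorder, and then diverges. The synopsis continues "depressive disorder, suicidal ideation or behavior, bipolar disorder, or schizophrenia". Section 9.3.2 continues "depressive disorder, bipolar disorder, or schizophrenia".

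Section 9.3 states the consequence of meeting a criterion: "Subjects who do not meet all inclusion criteria or do meet any exclusion criteria will not be eligible to receive study drug".

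**The concern.** Both versions of No. 8 are live text of the same protocol version, so this is not a difference between an amendment log and current wording. Eligibility is also fixed in the protocol and is not something left to the SAP. A site that works from the synopsis would turn away an adolescent with an old or passive ideation history. A site that works from Section 9.3.2 could randomize and dose the same adolescent. The C-SSRS is administered at Screening (Table 2), so ideation histories will come up and a rule will have to be applied, across about 30 sites. What is at stake is consistent application of a suicidality exclusion in a pediatric trial.

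**Working it through.** No arithmetic applies. The check sets the two v10.0 lists side by side and runs each type of history through Nos. 6 to 8.

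**Difference in wording.** Nos. 6 and 7 do not differ in substance between the lists. No. 8 differs by four words, present only in the synopsis: suicidal ideation or behavior.

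**Case check** (the 2-year limit read as applying to the eating disorders only, which is where it stands in the sentence):

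| History | Synopsis | Section 9.3.2 |
|---|---|---|
| Any past suicidal behavior | Excluded (Nos. 7, 8) | Excluded (No. 7) |
| Ideation with intent, at or within 6 months of Screening | Excluded (Nos. 6, 8) | Excluded (No. 6) |
| Ideation with intent, more than 6 months before Screening | Excluded (No. 8) | No specific criterion |
| Ideation without intent, at any time | Excluded (No. 8) | No specific criterion |

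The first two rows agree, so the behavior half of the phrase changes nothing. The last two rows are the conflict.

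**Alternative reading.** Suppose the 2-year limit is taken to cover all of No. 8. The lists then still disagree for ideation without intent at 0 to 24 months before Screening, and for ideation with intent at 6 to 24 months. The conflict shrinks but remains.

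**Internal consistency of the synopsis.** Under either reading, synopsis No. 8 already excludes everyone whose ideation would be caught by synopsis No. 6. The intent and 6-month limits in No. 6 then do no work. That suggests leftover text, but it does not prove it.

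**Earlier versions.** The same four-word mismatch is present in v8.0 and v9.0, where the psychiatric-history criterion in the body was No. 6. No revision-history entry gives a reason for it.

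**The case against.** **The body should govern.** The bar on study drug sits at the head of Section 9.3, directly above the body list, so Section 9.3.2 is the natural operative text and the synopsis phrase looks like a remnant. This narrows the ambiguity without removing it. There is no precedence clause, and here the synopsis is the stricter text, so defaulting to the body means dosing someone whom another page of the protocol excludes.

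**Other criteria catch these adolescents.** Both lists exclude "History or evidence of clinically significant disease (eg, malignancy, cardiac, respiratory, gastrointestinal, renal, or psychiatric disease", with some listed exceptions (No. 13), and anyone "Not suitable to participate in the study in the opinion of the investigator" (No. 28). Inclusion Nos. 1 and 4 ask for healthy subjects in stable health, and No. 8 removes depressive and bipolar disorders and schizophrenia in both lists. This stands as a limit on the size of the group. These general criteria rest largely on judgment, however, and appear in both lists, so they cannot settle a disagreement between two categorical rules.

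**Subjects are monitored.** The C-SSRS and PHQ-9 are scheduled from Week 1 onward. That limits the safety consequence but does not tell a site whom to enroll. Opposite decisions at two sites are a possibility rather than a demonstrated event, since the case report form guidelines are not shown.

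**Readings the documents do not support.** A reader might infer that membership of the per-protocol set is also left undefined, because that set requires no eligibility violations. Section 9.7.1.2 assigns the determination of per-protocol exclusions to the SAP, which is not at hand, so this cannot be counted. A reader might also infer from the v10.0 revision history that the two lists were meant to match word for word. That entry concerns the ordering and numbering of the body list only.

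**Conclusion.** The protocol contradicts itself on an operative eligibility rule and should be corrected. The contradiction is confined to adolescents with past ideation without intent, or with intent more than 6 months before Screening, who are not otherwise excluded under No. 13, No. 28 or the health inclusion criteria. They are ineligible under the synopsis and meet no specific exclusion in the body. The protocol gives no frequency for such histories, so no number of subjects can be stated.

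The effect is on who may receive study drug. There is none on the primary analysis, because the full analysis set takes all randomized subjects. The conclusion rests on the plain wording of v10.0 and on the absence of a precedence clause. It holds whichever way the 2-year limit in No. 8 is read.

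**What to change.** **Preferred.** Delete the four words on suicidal ideation or behavior from synopsis No. 8. Nos. 6 and 7 then govern in both lists, and the limits in No. 6 regain their purpose. The cost is one phrase. Visits, assessments, sample size and analysis do not change.

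**If the broader exclusion is what the sponsor wants.** Add the phrase to Section 9.3.2 No. 8 and delete No. 6 entirely from both lists, including its test on C-SSRS questions 4 or 5. Removing only the intent and 6-month limits would not work: No. 6 would then name any ideation but still identify it by the two questions that the criterion uses for ideation with intent. This route tightens eligibility in the body, so it needs a protocol amendment. Section 11.1 requires regulatory submission and ethics approval for amendments that affect subject safety or the scope of the study.
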